#### *Potential mediators*

The summary score of the different dimensions of illness representations (IPQ-R) and self-efficacy (CSA) are calculated and handled as continuous variable.

Mean and standard deviation are calculated for continuous variables. Multivariate analyses (inclusive multilevel analyses) are performed to determine time\*group differences for the continuous variables. Non-parametric tests are used if distributions are non-normal. In addition, descriptive statistics will be presented in median and (IQ) range. In all statistical analyses, a two-sided  $p<0.05$  is considered statistically significant.

Missing data analysis will be performed, meaning that the amount and nature of missing data will be studied and depending on this, adequate strategies to handle missing data will be applied (e.g. multilevel analyses). Patients are treated according to the intention to treat principles.

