#### 3.4 Sample size calculation

The composite weighted score consists of a summary score for worsening in functional status and the number of postoperative surgical complications, readmissions to the hospital and major adverse cardiac events (Table 2). The primary endpoint is partly adapted from the A-HeFT study.

The mean weighted score is estimated on 1.0 with a standard deviation of 0.9. This estimation is based on historical data of the UMCG (postoperative surgical complications and mortality), the Fitness Study - an on-going pilot study in the UMCG among the same population - (functional status), two literature studies: Iribarne et al., 2014 (hospital readmissions) and Serruys et al., 2008 (stroke and percutaneous interventions) and Meetbaar Beter database (re-interventions and myocardial infarction). A decrease of 0.3 means on average a decrease of one complication/event or worsening in functional status in 30% (or 10-20% decrease in major cardiac events or death) of the patients, which is considered to be clinically relevant. A group of 286 patients (143 in the PRE+POST group

and 143 in the POST group) achieve 80% power to detect a difference in the weighted score of 0.3, when alpha is set on 0.05.

The number of eligible patients is estimated to be 170 per year. We expect that 100 patients (60%) per year will be enrolled in the study. Therefore the estimated inclusion period is 3.5 years (n=350). In the total sample size (n = 350) a withdrawal of ±20% is incorporated. Because the mean score is estimated on different sources, different interim analyses are performed (section 7.4). Based on the interim analyses, the sample size can be adapted to ensure power.

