##### *Physical health*

Cardiorespiratory fitness will be measured by the six minutes walking test (6MWT). This submaximal walking test mimics efforts in everyday life of patients with coronary artery disease, because most of the daily life activities are performed submaximally. In addition, a walking test is close to a real life situation, since walking is an important activity of daily living. A strong correlation ( $r = 0.82$ ,  $p < 0.001$ ) with VO2peak was shown by Tueller and colleagues (2010), however other studies found a modest correlation between the 6MWT and maximal oxygen uptake (VO2max, 0.6-0.7). From a meta-analysis strong evidence was found that the 6MWT was responsive to change in clinical status following cardiac rehabilitation. However, an increase in percentage between 2-8% should be taken into account, when the test is repeated. In addition, cardiorespiratory fitness is measured using results of the bicycle tests (oxygen uptake, heart rate and work load) which are performed in the context of the cardiac rehabilitation programs.

Muscle strength will be assessed with two hand dynameters. Grip strength will be bimanually measured with a JamarR Hydraulic Hand dynameter as measure for muscle strength of the upper extremities. Normative data of the grip strength test and 6MWT have been reported by Tveten and colleagues (2014).

For measuring isometric muscle strength (knee extension) the Q force is used. It consists of a chair with an attached, adjustable fixed leg brace at the front. It has three sensors, which are located in the brace to determine the generated force in Newton, the angle between the horizontal chair surface and the brace and the distance between the force transducer and the rotation axle of the brace in millimeter. Rails are attached at the left and

right bottom of the seat to which the brace is connected so that both the left and right leg can be tested (Figure 3).

Table 2: definitions of the composite weighted primary endpoint

Functional status	Score
Worsening in physical functioning (domain score of health related quality of life, rand36_v2)	1
No change or improvement in physical functioning	0
Worsening in physical problem (domain score of health related quality of life, rand36_v2)	1
No change or improvement in physical problem	0

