## 9. STATISTICAL ANALYSIS

### 9.1 Primary study parameter(s)

The primary endpoint is a composite score of functional status, postoperative surgical complications, hospital readmission and MACE. The summary score is calculated for each patient according to Table 2. Missing data on quality of life will be filled with the worst-case score for that component in the analysis. The mean and standard deviation for the summary scores of each group are calculated and handled as a continue variable. Multivariate analyses, inclusive multilevel analyses, are performed to determine time\*group differences at three months and one year after surgery.

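### The time-by-group models do not prespecify adjustment for the pre-randomisation T1 value, which gives up precision that costs nothing to recover

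*Combined protocol and SAP*

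**What the plan says.** - **Primary score (section 9.1).** "The summary score is calculated for each patient according to Table 2". The score is treated as continuous and analysed by multivariate, including multilevel, methods for time-by-group differences at three months and one year. No covariate is named.
- **Continuous secondary outcomes (section 9.2, closing paragraphs under Potential mediators).** "Multivariate analyses (inclusive multilevel analyses) are performed to determine time" by group differences. Again no covariate is named.
- **Fitness outcomes (section 9.2, Physical capacity).** T1 is listed with the later visits as one of the time points of the outcome.
- **Timing (sections 7.2 and 7.3).** Allocation follows the T1 measurements. RAND-36, PHQ-9 and GAD at T1 are already part of standard care.
- **Primary score items (Table 2).** Two of the items are one-point scores for decline in a RAND-36 domain, for example "Worsening in physical functioning (domain score of health related quality of life". The remaining items are clinical events.
- **Adjustment (section 9.3).** If the arms are found to differ at baseline, results are to be read with caution and the methods may be changed to adjust. This is the only text on baseline adjustment.
- **Sample size (section 3.4).** "The mean weighted score is estimated on 1.0 with a standard deviation of 0.9". No allowance is made for covariates.

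**The concern.** T1 is measured before allocation, so it cannot be affected by treatment. It probably correlates with the later value of the same measure. Leaving it out of the model, or entering it as a response with arm means free to differ at T1, gives wider confidence intervals than the data allow. This affects walk distance, strength, PHQ-9, GAD-7, the RAND-36 scales, self-efficacy, illness perception and any activity measure that is analysed by model.

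The section 9.3 rule does not fill the gap. It decides on adjustment after baseline differences have been seen, and it names neither the covariates nor the model. The adjusted analysis would therefore be chosen on the data.

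For the primary score, a patient with a high T1 score has more room to decline and, through regression to the mean, is more likely to. A patient near the floor can hardly lose the minimal change. T1 should therefore predict the two decline points to some degree.

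**Working it through.** **Step 1. Reproduce the plan's figure.** Section 3.4 gives SD 0.9, difference 0.3, alpha 0.05 and 80% power ("achieve 80% power to detect a difference in the weighted score of 0.3, when alpha is set on 0.05"). Section 9.2 sets two-sided testing.

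n per arm = 2 x (1.960 + 0.842)^2 x 0.9^2 / 0.3^2 = 141.3, so 142. The t-test version gives 142.2, so 143, which matches "A group of 286 patients (143 in the PRE+POST group" and the same number in the POST arm. Power at 143 per arm is 80.5% (normal) or 80.2% (t). The stated size reproduces with no covariate.

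**Step 2. Continuous outcomes.** Take equal variances at T1 and follow-up and a correlation rho between them. The documents give no rho, so 0.4 to 0.7 is an assumption. Variances relative to a single follow-up value are:

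- follow-up only: 1
- change from T1: 2(1-rho)
- T1 as covariate: 1-rho^2
- covariate against change: (1-rho^2)/(2(1-rho)) = (1+rho)/2

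| rho | change | T1 covariate | covariate / change | 143 per arm adjusted is worth, in change scores |
|---|---|---|---|---|
| 0.4 | 1.20 | 0.84 | 0.70 | 143/0.70 = 204 |
| 0.5 | 1.00 | 0.75 | 0.75 | 143/0.75 = 191 |
| 0.6 | 0.80 | 0.64 | 0.80 | 143/0.80 = 179 |
| 0.7 | 0.60 | 0.51 | 0.85 | 143/0.85 = 168 |

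Against change scores, adjustment is worth a sample 18% (1/0.85) to 43% (1/0.70) larger. Against follow-up values alone, the third column is itself the variance ratio: 0.84 down to 0.51.

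**Step 3. Does a time-by-group model give the change-score contrast?** I used one simulated complete data set with two time points, 143 per arm and rho 0.6. A multilevel model with arm means free at T1 gave an interaction of 0.2167, identical to the difference in mean change, with standard error 0.104. Using T1 as covariate, or constraining the arm means to be equal at T1, gave standard error 0.094 in both cases. The squared ratio from the unrounded errors is (0.0938/0.1045)^2 = 0.81, against 0.80 from the formula. Over 4,000 simulated trials the covariate-to-change ratio was 0.669/0.843 = 0.79.

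**Step 4. Primary score.** If the two T1 RAND-36 scores explain a share R2 of the total-score variance, the SD becomes 0.9 x sqrt(1-R2), and power = Phi(0.3/(SD x sqrt(2/143)) - 1.96):

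| R2 | SD | power at 143 per arm (normal) |
|---|---|---|
| 0 | 0.900 | 80.5% |
| 0.02 | 0.891 | 81.3% |
| 0.05 | 0.877 | 82.4% |
| 0.10 | 0.854 | 84.4% |
| 0.15 | 0.830 | 86.4% |

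The size of R2 has to be assumed. I simulated two normal domains with inter-domain correlation 0.6, rho 0.4 to 0.8, a threshold of 0.5 SD and mean improvement of 0 to 0.6 SD. T1 explained about 3% to 21% of the variance of the two decline points, and about 0.3% to 16% of the total-score variance (0.9^2 = 0.81). With scores clipped at the ends of the scale, the ranges were about 3% to 17% and 1% to 13%. For R2 of 0.01 and 0.13 the t-test power is 80.6% and 85.4%, against 80.2% unadjusted.

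**The case against.** **The plan does not say change scores.** A reader might infer that the continuous outcomes are to be compared as changes from T1. The documents do not state this. A multilevel model with equal arm means at T1 fits the wording of 9.1 and 9.2 and would already be about as efficient as covariate adjustment. This stands: the 0.70 to 0.85 ratio applies if T1 enters as a free response. Listing T1 among the fitness time points implies that reading but does not settle it. The constraint is written nowhere, though, and a follow-up-only comparison would also gain from adjustment.

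**T1 does not govern the primary score.** A reader might infer that the T1 RAND-36 values largely determine the decline points, or that the score ignores baseline. Neither is supported. The points presumably take T1 as their reference, so baseline is built into the score and is only left unadjusted. T1 explained a minority of the points in the simulations, and they sit beside eleven event items. The threshold comes from a cited source and is not stated. The simulations also leave out the worst-case fill for missing quality of life, which may dilute the relation.

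**Adjustment is not wholly absent.** Section 9.3 permits it. That is true, but it is optional and data-driven.

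**Reach.** The gain does not extend to the chi-square, Mann-Whitney or other non-parametric comparisons. Nor is complete T1 data assured: the take-home questionnaires and the armband come back about a week later (section 7.3). Both points stand.

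**Conclusion.** The point holds as one of efficiency and prespecification. Sections 9.1 and 9.2 do not say how T1 enters the time-by-group models, and section 9.3 leaves adjustment to what the baseline data show.

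For continuous outcomes measured at T1 and analysed by model, the gain is material: variance falls to 0.70-0.85 of the change-score value, or to 1-rho^2 of the follow-up-only value. This rests on assumed correlations of 0.4 to 0.7. If the intended model already holds the arm means equal at T1, the gain is in place and only the wording is missing.

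For the primary score the gain is small, from about 80% power to about 80.5-85% at 143 per arm. The correlations and the threshold behind that range are assumed.

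A reader might conclude that the trial is biased or underpowered for want of this adjustment. The documents do not support that: randomisation protects the unadjusted comparison, and the stated 143 per arm gives 80% power on the plan's own inputs.

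**What to change.** - **Section 9.2.** For each continuous outcome measured at T1 and analysed by model, prespecify either the T1 value as a covariate with only post-allocation visits as responses, or a multilevel model with T1 as a response and arm means constrained equal at T1. The second also keeps patients whose T1 value is missing; if the first is chosen, state a rule for missing T1. Use T1 and not T2 as the baseline, because T2 follows the preoperative programme in one arm.
- **Section 9.1.** Add the T1 RAND-36 physical functioning and physical problem scores as prespecified covariates of the primary model.
- **Section 9.3.** Replace the adjustment that depends on finding baseline differences with the fixed covariate set above. The stratification factors (type of surgery, gender, age) could be named in the same edit.

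The cost is analysis-plan wording, settled before outcome data are compared by arm. No new data, visits or patients are needed, and the sample size need not change.

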#### **9.3 Other study parameters**

A multivariate analysis of variance (MANOVA) is performed for continue baseline parameters (age, BMI, anxiety for surgery etc.) and surgery parameters (such as waiting time, surgery duration). Non-parametric tests (mann whitney test or kruskall-wallis test) are used to test differences, when data is not normally distributed and for ordinal variables (such as type of surgery). Possible differences of binary parameters (such as gender) are tested with chi-square test. If baseline differences are found, caution will be taken when interpreting the results of the primary and secondary endpoints and methods may be modified to adjust for difference.

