### 7.2 Randomisation, blinding and treatment allocation

Patients are randomly assigned to one of two CR programs in a 1:1 ratio. Allocation to the PRE+POST group or POST group will occur after baseline measurements. Blocked randomization is used to ensure continued inclusion rates in both CR programs.

Randomization is stratified for type of surgery (CABG, AVR, AVR+CABG and other), gender and age ( $\geq 65$  years and  $< 65$  years). Medical staff and researchers are not blinded, because of the complex logistics of the PRE+POST CR program.

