#### *Heart-ROCQ registry*

Data of patients who did not participate, but have given written consent for using routinely collected data, are collected in the Heart-ROCQ registry. Data from the Heart-ROCQ registry are not used for the primary statistical analyses. Separate analyses are performed between included study patients and patients of the Heart-ROCQ registry to get insights into the generalizability of the results of this study. These separate analyses consist of a multivariate analysis of variance (MANOVA) (continue routinely collected baseline parameters (e.g. age, BMI, anxiety for surgery etc.), non-parametric tests (mann whitney test or kruskall-wallis test) for non-normal distributed or ordinal variables (e.g. type of surgery) and chi-square tests for binary parameters (e.g. gender). The included study patients are representative when there are no differences shown with the study registry.

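### Type of surgery is a nominal variable but is assigned to rank tests as if ordinal, so the result depends on arbitrary coding and real differences in surgical mix can be missed, mainly in the registry comparison

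*Combined protocol and SAP*

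**What the plan says.** Section 9.3 (Other study parameters) sets out how baseline and surgery parameters are compared between the arms. Continuous variables go to MANOVA. Mann-Whitney or Kruskal-Wallis tests are used "when data is not normally distributed and for ordinal variables (such as type of surgery"). Chi-square is reserved for two-category variables: "Possible differences of binary parameters (such as gender) are tested with chi-square test". If a difference is found, the results are read with caution and "methods may be modified to adjust for difference".

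The Heart-ROCQ registry paragraph of the same section uses the same scheme to compare trial participants with patients who declined but allowed use of their routine data. It plans "non-parametric tests (mann whitney test or kruskall-wallis test) for non-normal distributed or ordinal variables (e.g. type of surgery"), again with chi-square for binary parameters only. It then gives a decision rule: "The included study patients are representative when there are no differences shown with the study registry".

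The categories appear in section 7.2: "Randomization is stratified for type of surgery (CABG, AVR, AVR+CABG and other), gender and age". No section defines a ranking or numerical coding for them.

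**The concern.** CABG, AVR, AVR+CABG and other are kinds of operation, not steps on a scale. One could argue that the combined procedure is heavier than either single one, but CABG and AVR have no agreed order and *other* has no position at all. A rank test asks whether one group tends to have higher codes than the other. If the codes are arbitrary, so is that question. Two analysts who number the categories differently can reach opposite conclusions from the same table, and some differences in mix cancel out in the rank sum.

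Type of surgery is the only ordinal variable that the plan names, in both places, so this is the stated method for that variable. The protocol itself treats the variable as important. The Summary names the type of procedure as a main source of perioperative risk, and section 7.1.2 lists it among the parameters that may influence the outcomes. At stake is whether the registry comparison can do its job, which section 7.3 describes as giving insight into possible selection bias and generalisability.

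**Working it through.** **Figures in the plan.** The documents give none for this comparison. The sample size in section 3.4 is not in dispute: 2 × (1.96 + 0.84)² × 0.9² / 0.3² ≈ 142 per arm, and the t-test version gives 142.2, so 143 as stated. It is used here only for group sizes.

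**Inputs.**
- Trial patients: 350 (section 3.4).
- Registry patients: not stated. Section 3.4 expects 170 eligible and 100 enrolled a year for 3.5 years, so at most (170 − 100) × 3.5 = 245 non-participants. I use 240 (nearly all consent) and 150 (about 61% consent, 150/245). Both are assumptions.
- Surgical mix: not stated. All mixes are assumptions, in the order CABG / AVR / AVR+CABG / other.
- Two-sided 0.05 (section 9.2).

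**Step 1: one table, different codings.** Assume trial counts 158/70/52/70 (n = 350) and registry counts 132/24/12/72 (n = 240), which is about 45/20/15/20% against 55/10/5/30%.

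Chi-square: category totals are 290/94/64/142. Expected trial counts (total × 350/590) are 172.0/55.8/38.0/84.2, and expected registry counts are 118.0/38.2/26.0/57.8. The sum of (observed − expected)²/expected is 12.37 + 18.05 = 30.42 on 3 df, p = 0.000001, whatever the order.

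Rank test: W is the sum over categories of trial count × midrank, with mean 350 × 591/2 = 103,425. Its variance is (n₁n₂/12) × [(N + 1) − Σ(t³ − t)/(N(N − 1))], giving SD 1,888.4. The variance depends only on the category totals t, so it is the same for every order.
- Listed order: midranks 145.5/337.5/416.5/519.5, W = 104,637, z = 0.64, p = 0.52.
- Order AVR+CABG, AVR, CABG, other: midranks 32.5/111.5/303.5/519.5, W = 93,813, z = −5.09, p = 0.0000004.

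Reversing an order leaves the two-sided p unchanged, so there are 4!/2 = 12 distinct orderings. Over these, p runs from 0.0000004 to 0.67; eight fall below 0.05 and four do not. With two groups, Kruskal-Wallis gives the same p as Mann-Whitney.

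**Step 2: power.** Multinomial samples were simulated and tested with the tie-corrected Mann-Whitney test and with Pearson chi-square on the 2 × 4 table.

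| Assumed mix, trial vs registry (%) | Sizes | Rank test, listed order | Rank test, 12 orderings (median) | Chi-square |
|---|---|---|---|---|
| 50/20/10/20 vs 40/35/10/15 | 350 vs 150 | 11% | 11% to 89% (72%) | 87% |
| 45/25/15/15 vs 55/10/10/25 | 350 vs 150 | 8% | 8% to 99.7% (about 70%) | 99% |
| 50/20/10/20 vs 40/35/10/15 | 350 vs 240 | 14% | not shown | 95% |
| 45/25/15/15 vs 55/10/10/25 | 350 vs 240 | 8% | not shown | 99.9% |
| 45/20/15/20 vs 30/20/15/35 | 350 vs 240 | 99% | 55% to 99% | 98% |

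In the first two mixes the change sits largely in the middle categories and the listed order is the worst of the 12. In the last mix patients move from the first category to the last, so the shift follows the coding and the rank test does slightly better than chi-square. With no true difference, both tests reject in about 5% of runs. The fault is erratic sensitivity, not excess false positives.

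**The case against.** Four points can be made on the other side.

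1. A reader might infer that a difference in surgical mix would usually be missed. The documents do not support that. They give neither mix nor coding; the low figures above come from the least favourable ordering, median power over orderings is about 70%, and some shifts are detected as well as by chi-square. Only *can be missed* is supported. This objection stands.

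2. A reader might infer that the between-arm baseline comparison is compromised, or that the error reaches the primary result. It does not. Randomisation is blocked and stratified by type of surgery (section 7.2), so arm differences are due to chance and limited by design, and the plan only calls for caution and possible adjustment. A residual imbalance, for example after withdrawals, could go unflagged, but that is a small matter. This objection stands too.

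3. The registry comparison is exploratory, stays outside the primary analyses and covers several variables, so missing one difference does not by itself make the study representative. That is fair and limits the severity. But a comparison meant to reveal selection should not depend on undefined numbering for one of its main clinical variables.

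4. The false reassurance also comes from reading a non-significant result as proof of representativeness, which chi-square does not cure: in the first scenario it still misses 13% of real differences. This is correct, but it is a separate weakness and does not justify a rank test on a nominal variable.

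**Conclusion.** The rule is wrong as written in both places. Type of surgery is nominal, no coding is defined, and the assigned test can give a different answer for each numbering of the same data. Real differences in surgical mix can therefore be missed. How often depends on the true mix and the chosen coding: rank-test power runs from about 11% to 89% in one assumed scenario and from about 8% to 99.7% in another, against a fixed 87% and 99% for chi-square (350 against 150 patients).

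The consequence is confined mainly to the registry comparison, where allocation is not random and the absence of a shown difference is taken as representativeness. Severity is minor. The mixes and registry sizes are assumptions, but the dependence on coding needs neither: it follows from applying a rank test to unordered categories.

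**What to change.** In section 9.3 and in the registry paragraph:

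- Remove type of surgery as the example of an ordinal variable and call it nominal.
- Extend the chi-square test from binary to categorical parameters. For type of surgery, apply it to the four categories of section 7.2, with the Fisher-Freeman-Halton test if cells are sparse.
- Report the percentage in each category for both groups, so that the reader can judge the size of any difference.
- Keep the rank tests for truly ordinal or non-normally distributed variables.

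The edit is a few sentences in two places. It needs no new data, changes no other analysis and can be made before any data are analysed. The one trade-off is that chi-square can be slightly less powerful when a shift happens to follow the coding (98% against 99% in the example), which is negligible.
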